7.3. Subject Withdrawal

Subjects who are screen failures may be eligible for rescreening only if rescreening is approved by the Medical Monitor.

A subject may be discontinued from the study at any time if the subject, Investigator, or Sponsor determines that it is not in the best interest of the subject to continue participation. Reasons for discontinuation include:

- Adverse event
- Lost to follow-up
- Withdrawal by subject
- Non-compliance with study drug
- Physician decision
- Pregnancy
- Protocol deviation
- Study terminated by Sponsor
- Other

If a subject withdraws from the study for any reason, any ongoing adverse events (AEs) will be followed until resolution, until deemed stable by the Investigator, or until the subject is deemed by the Investigator to be lost to follow-up. If, in the opinion of the Investigator, it is necessary to monitor a subject beyond the Safety Follow-up visit, the Follow-up period may be extended as necessary. In such instances, the Sponsor and the Investigator will agree to an acceptable follow-up schedule.

In the event that a subject chooses to withdraw from the study, the Investigator should make a reasonable effort to ascertain the reason(s) for withdrawal, while fully respecting the subject's rights. Subjects are to be asked to return to the clinic for an Early Termination visit and a 2-week postdiscontinuation Safety Follow-up visit. The Early Termination visit should be scheduled as close as possible to the subject's last dose of study drug. If the subject fails or refuses to return to the study site, an attempt must be made to contact the subject by telephone in order to assess as many safety parameters as possible. All data collected over the telephone must be documented and kept in the subject's record.

The Investigator must maintain a record of all subjects who fail to complete the study. The reason for study discontinuation will be documented and made on the appropriate electronic case

report form (eCRF). If a subject is lost to follow-up, a reasonable attempt to contact the subject must be made and documented.

The study may continue for a planned period of up to 68 weeks and/or until regulatory approval has been obtained, and the product is commercially available and reimbursed.

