8.2. Schedule of Visits and Assessments

Eligibility criteria and assessments described in [Section 8.3](#) will occur on Day 1 of the study.

For a missed visit, the study site should attempt to contact the subject to reschedule.

Subjects who discontinue from the study prematurely will be encouraged to return for an Early Termination visit and a 2-week postdiscontinuation Follow-up visit. See [Section 7.3](#) for additional details.

See [Table 3](#) for a full schedule of assessments.

Table 3: Schedule of Assessments

	Screening Visit Transition from Previous Study ^{a, b, c}	Week 1	Week 2	Week 6	Week 12	Visits every 8 Weeks (Weeks 20, 28, 36, 44, 52, 60)	Week 68 EOT/ET Visit ^d	Safety Follow-Up Visit
Day	SCN/1	8 (±4)	15 (±4)	43 (±4)	85 (±4)	Every 56 (±4) days	477 (±4)	14 (±4) days after the final dose of study drug
Visit	1	2	3	4	5	6, 7, 8, 9, 10, 11	12	13
Informed Consent	X							
Qualification/ Diagnostic Assessments								
Eligibility Review	X							
Medical and Psychiatric History Updates	X							
Qualification/ Safety Assessments								
Symptom-driven Physical Examination	X							
Urine Pregnancy Test (all women)	X	X	X	X	X	X	X	X
Urine Drug Screen ^e	X							
C-SSRS (since last visit)	X	X	X	X	X	X	X	X
Adverse Event Monitoring	X	X	X	X	X	X	X	X
Concomitant Medication Review	X	X	X	X	X	X	X	X
Additional Study Procedures								
Dispensation of Study Drug ^f	X	X	X	X	X	X		
Study Drug Adherence Review ^g		X	X	X	X	X	X	

Abbreviations: AE=adverse event; C-SSRS=Columbia-Suicide Severity Rating Scale; EOT=end of treatment; ET=early termination; SCN=Screening

- ^a Screening (Visit 1) may occur on the same day as the Safety Follow-up Visit of the preceding Study ALK5461-217, in which case the procedures of these two visits may be combined.
- ^b Procedures already performed in ALK5461-217 do not need to be repeated in ALK5461-218. Information from the antecedent study will be re-entered into the electronic data capture system for Study ALK5461-218.
- ^c If the subject is screened ≥ 30 days after completing ALK5461-217, Investigators will review key eligibility criteria in order to ensure subject still meets requirements (Sample checklist is provided in [Section 20](#), Appendix A).
- ^d ET visit should occur as close as possible to subject's last dose.
- ^e Urine drug screen testing will be performed at Visit 1 and at subsequent visits as needed based on the Investigator's judgment.

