13.4. Monitoring and Recording of Adverse Events

Adverse event data collection will begin after a subject signs the ICF and will continue until completion of the Safety Follow-up visit or 2 weeks after the final dose of study drug. Any AE or SAE having an onset after the Safety Follow-up visit will not be collected or reported unless the Investigator feels that the event may be related to the study drug.

Subjects will be instructed by the Investigator or designee to report the occurrence of any AE. All volunteered, elicited, and observed AEs are to be recorded on the AE eCRFs.

The Investigator will assess all AEs regarding any causal relationship to the study drug (see [Section 13.3](#)), the intensity (severity) of the event, action taken, and subject outcome.

The following criteria should be used to guide the assessment of intensity (severity):

- **Mild:** causes awareness of sign or symptom but is easily tolerated; does not interfere with usual activities
- **Moderate:** causes discomfort enough to interfere with usual activities
- **Severe:** is incapacitating; results in inability to work or perform usual activities

All AEs will be followed until resolution, until deemed stable by the Investigator, or until the subject is deemed by the Investigator to be lost to follow-up.

For clinical study safety reporting purposes, the most recent version of the Investigator's Brochure will be used as the reference document to designate event expectedness.

Withdrawal from the study as a result of an AE, and any therapeutic measures that are taken, shall be at the discretion of the Investigator. If a subject withdraws from the study for any reason, any ongoing AEs will be followed until resolution, until deemed stable by the Investigator, or until the subject is deemed by the Investigator to be lost to follow-up.

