1.2. Summary of the Study Design and Schedule of Assessments

This is an open-label, Phase 3b, multicenter extension study to evaluate the long-term safety and tolerability of ALKS 5461 administration for use as an adjunctive therapy to antidepressants for the treatment of refractory MDD. Subjects who complete participation in the ALK5461-217 study will be eligible for enrollment into the study.

At Visit 1 (day 1), all eligible, consenting subjects will begin the treatment period. One tablet will be taken sublingual on each dosing day. From Day 1 onward, all participating subjects will take ALKS 5461 2/2 mg and an approved antidepressant therapy (ADT).

Study staff will administer the first dose of ALKS 5461 on Day 1. From that point on during the treatment period, the staff will dispense ALKS 5461 for subjects' self-administration. Subjects will be advised to take the study drug at bedtime.

During the treatment period, subjects will return to the clinic for periodic scheduled visits, at which time safety and tolerability will be assessed, as well as a 2-week post-discontinuation Follow-up visit.

For a missed visit, the study site should attempt to contact the subject to reschedule. Subjects who discontinue from the study prematurely will be encouraged to return for an Early Termination visit and a 2-week post-discontinuation Follow-up visit.

Subjects' demographic data will be carried over from the ALK5461-217 study. If ≥ 30 days have elapsed since end-of-treatment in ALK5461-217, medical and psychiatric history for the intervening period will be queried and updated in the ALK5461-218 database as necessary.

[figure not shown]
At each visit, subjects will be asked about the medications they have taken since the last visit.

Drug adherence for ALKS 5461 will be reviewed with subjects at each visit.

Please refer to the protocol for a detailed schedule of assessments. A brief schematic of study design is provided in Figure 1. A summary of the schedule of safety assessments is presented in

Table 1.

Figure 1: Study Design Schematic

Abbreviations: EOS=end of study; EOT=end of treatment; ET=early termination

Table 1: Schedule of Safety Assessments

Procedure or Assessment	Schedule
Dispensation of study drug	All scheduled visits prior to End of Treatment or Early Termination Visit (i.e., Screening [Day 1], weeks 1, 2, 6, 12, 20, 28, 36, 44, 52, 60)

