3.2. Study Population

3.2.1. Definitions of Analysis Populations

Safety Population will consist of all enrolled subjects who received at least 1 dose of study drug in the ALK5461-218 study.

Post-discontinuation Safety Population will consist of subjects who received at least 1 dose of study drug in the ALK5461-218 study, and met one of the following criteria:

- Subjects who entered the Post-discontinuation Period and had a Post-discontinuation Follow-up Visit
- Subjects who did not enter the Post-discontinuation Period (i.e., final visit was last visit in treatment period), but had at least 1 PDEAE reported
- Subjects who died after either completing the treatment or having an Early Termination (ET) Visit

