3.6. Safety Analysis

3.6.1. General Considerations

All safety endpoints will be summarized based on observed data for the Safety Population during the Treatment Period / during the Post-discontinuation Safety Period.

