3.6.2. Adverse Events

Adverse events will be coded by System Organ Class (SOC) and Preferred Term using the Medical Dictionary for Regulatory Activities (MedDRA, version 20.0). The verbatim term will be included in the AE listings.

An AE will be considered as a treatment-emergent adverse event (TEAE) if it starts or worsens (if present during baseline period) on or after first dose date during the treatment period (defined as the period between the first dose date and last dose date +1). An AE will be considered as a PDEAE if it starts during the Post-discontinuation Safety Period (defined as after the period after last dose date plus 2 days, inclusive, and include AEs with preferred terms that may have also

been TEAEs during the Treatment Period. For the determination of TEAEs during the treatment period, AEs with the greatest severity before the baseline will be used as the benchmark for the comparison of the AEs occurring during the treatment period. For PDEAEs, all AEs starting during the Post-discontinuation Safety Period will be summarized.

All AEs will be listed by subject. TEAEs / PDEAEs, deaths, serious adverse events (SAEs), and AEs leading to study discontinuation will be included in the summary tables. For AEs leading to study discontinuation or deaths, the AEs will be summarized in the period in which the discontinuation or death occurred. Drug-related TEAEs include those scored as definitely related, probably related, and possibly related by the investigator.

The following summary tables will be produced for the treatment period / Post-discontinuation Safety Period for the Safety Population:

- Overview AE summary tables (TEAEs / PDEAEs)
- TEAEs / PDEAEs by System Organ Class and Preferred Term
- TEAEs / PDEAEs by Preferred Term
- TEAEs / PDEAEs experienced by $\geq 5\%$ of subjects by Preferred Term
- TEAEs / PDEAEs by System Organ Class, Preferred Term, and Severity
- Drug-related TEAEs by Preferred Term
- SAEs (fatal and non-fatal) by Preferred Term
- AEs leading to study discontinuation by System Organ Class and Preferred Term
- AEs leading to study discontinuation by Preferred Term

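### The SAP defines a Post-discontinuation Safety Population but puts the post-discontinuation AE tables on the full Safety Population, which understates percentages if follow-up and event capture are incomplete

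*SAP*

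**What the plan says.** SAP 3.2.1 defines two analysis sets. The Safety Population is everyone enrolled and dosed at least once. The Post-discontinuation Safety Population is the dosed subjects who meet one of three criteria: (1) they entered the post-discontinuation period and had the Follow-up Visit; (2) "Subjects who did not enter the Post-discontinuation Period (i.e., final visit was last visit in treatment period), but had at least 1 PDEAE reported"; or (3) they died after completing treatment or after an Early Termination visit.

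SAP 3.2.2 starts the post-discontinuation period two days after the last dose and ends it at the end-of-study date.

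The analysis sections then name only the first set. SAP 3.6.1: "All safety endpoints will be summarized based on observed data for the Safety Population during the Treatment Period / during the Post-discontinuation Safety Period". SAP 3.6.2, introducing the AE tables: "The following summary tables will be produced for the treatment period / Post-discontinuation Safety Period for the Safety Population". That list includes PDEAEs by system organ class and preferred term, by preferred term, by severity, and a table limited to terms reaching 5% of subjects. Disposition (SAP 3.2.3) counts the Safety Population and no other analysis set. Protocol 14.2.1 defines only a Safety Population.

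On follow-up, SAP 1.2 says: "Subjects who discontinue from the study prematurely will be encouraged to return for an Early Termination visit and a 2-week post-discontinuation Follow-up visit".

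**The concern.** A population tailored to the period after stopping is defined and then not used for that period. The choice affects the percentages. The Safety Population includes subjects whose observation ended at or near the last dose. They could not show a post-discontinuation event unless someone reported it later, yet each counts as a subject without one.

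The plan itself foresees that some subjects will not return. Early discontinuers are encouraged to attend, and Protocol 7.3 provides for those who fail or refuse to do so.

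At stake is the description of what happens after a daily opioid-modulating tablet is stopped. The synopsis names the two-week follow-up as part of the safety evaluation, and safety and tolerability are the study's only objective. A reader of the PDEAE tables would see a percentage without knowing how many subjects were observed.

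**Working it through.** The plan states no figure on this point, so there is none to reproduce. The check is textual, followed by arithmetic on assumed follow-up.

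**1. Where the defined population is used.** In the supplied SAP its name appears only in its definition in 3.2.1. Sections 3.6.1 and 3.6.2 use a similar term, Post-discontinuation Safety Period, but that is a time interval. The population named beside it is the Safety Population.

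**2. The numerator.** A subject with a PDEAE either had the Follow-up Visit (criterion 1) or had a last visit within the treatment period and a PDEAE reported (criterion 2). The count of subjects with a given PDEAE is therefore essentially the same in both populations. Only the denominator changes.

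**3. Effect on a percentage and on the 5% table.** Inputs: N = 250 (planned maximum, SAP 2); D = size of the defined population, not given in the documents and here assumed to be 225 or 175 (90% or 70% of 250); k = subjects with the term.

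- Safety Population percentage = 100k/250. Defined-population percentage = 100k/D. Their ratio is D/250.
- Smallest k that enters the 5% table = 0.05 × denominator, rounded up.

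| Denominator | 0.05 × denominator | Smallest k | That k as a percentage | k = 10 as a percentage |
|---|---|---|---|---|
| 250 | 12.5 | 13 | 5.2% | 4.0% |
| 225 | 11.25 | 12 | 5.3% | 4.4% |
| 175 | 8.75 | 9 | 5.1% | 5.7% |

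If D = 225, a term with exactly 12 subjects is left out of the 5% table on the Safety Population but would enter it on the defined one. If D = 175, the same holds for terms with 9 to 12 subjects. If D = 250, nothing changes.

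**4. Which denominator is nearer the true risk.** Assume a 10% risk in every subject and no deaths. F subjects are followed, and a fraction r of the events in the other 250 − F subjects is reported. Events in unfollowed subjects = 0.10 × (250 − F) × r. The numerator is 0.10F plus those events. The defined population is F plus those events, because criterion 2 admits exactly those subjects.

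| F | r | Safety Population | Defined population |
|---|---|---|---|
| 175 | 0 | 17.5/250 = 7.0% | 17.5/175 = 10.0% |
| 175 | 1 | 25/250 = 10.0% | 25/182.5 = 13.7% |
| 225 | 0 | 22.5/250 = 9.0% | 22.5/225 = 10.0% |
| 225 | 1 | 25/250 = 10.0% | 25/227.5 = 11.0% |

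The Safety Population is low when unfollowed subjects' events are missed, and exact when they are all captured. The defined population is exact when they are missed and high when they are captured, because criterion 2 adds such subjects only if they had an event. Criterion 3 selects on death in the same way.

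**The case against.** **The text may already restrict the denominator.** SAP 3.6.1 refers to observed data, and SAP 7.1 says that missing values are not imputed. Neither statement changes the denominator, and 3.6.1 names the Safety Population in the same sentence. The slash wording may be shorthand for a matching pair of period and population. The mock tables and programming specifications are separate documents, not seen here, and may name the defined population. If they do, they conflict with 3.6.1 and 3.6.2, and the same wording change is needed.

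**Follow-up may be nearly complete.** Protocol 7.3 asks withdrawing subjects to return and adds: "If the subject fails or refuses to return to the study site, an attempt must be made to contact the subject by telephone". Under Protocol 13.4, AE collection "will continue until completion of the Safety Follow-up visit or 2 weeks after the final dose of study drug". These provisions may capture most events. This stands: with full capture the Safety Population percentage is the correct whole-group figure. A reader might infer that the PDEAE tables will certainly understate risk. The documents do not support that, because they give neither a follow-up rate nor a capture rate.

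**The defined population is imperfect too.** This also stands (step 4 of the working). A reader might infer that the population should be rebuilt, for example around the follow-up window of "14 (±4) days after the final dose of study drug" with telephone contacts counted. The documents do not support going that far. Criterion 1 sets no day limit. Protocol 7.3 requires telephone data to be kept in the subject's record, but does not say that they reach the database. Moving reported events of excluded subjects out of the tables would conflict with SAP 3.6.2, which summarizes every AE that starts in the period. Keeping the death criterion would still leave selection on outcome.

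**Conclusion.** The inconsistency is real within the supplied SAP: a population is defined for the post-discontinuation period, and the tables for that period name another. As written, PDEAE percentages are understated to the extent that follow-up is incomplete and events in unfollowed subjects go unreported, and not otherwise. The size is unknown. The shift in the 5% cut-off from 13 subjects to 12 or 9 rests on an assumed 250 dosed and an assumed defined population of 225 or 175. The comparison with true risk also assumes a 10% risk that is equal in followed and unfollowed subjects.

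Severity is minor. No test or sample size depends on this. All AEs are listed, and the PDEAE tables by system organ class and preferred term, and by preferred term, have no cut-off. The count of study completers and the post-discontinuation C-SSRS summary may already give readers a rough idea of how many subjects were followed.

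**What to change.** - In SAP 3.6.1 and 3.6.2, keep the Safety Population for the treatment-period tables. Name the Post-discontinuation Safety Population, as 3.2.1 already defines it, as the denominator for the PDEAE tables. Reported PDEAEs then stay tabulated, as 3.6.2 requires.
- In SAP 3.2.3, add the size of that population to the disposition table, split into subjects with a Follow-up Visit and subjects admitted only by criterion 2 (PDEAE reported) or criterion 3 (death).
- Footnote the PDEAE tables: criteria 2 and 3 select on outcome, so the percentage may be somewhat high if follow-up is incomplete.

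The cost is a few words of SAP text, the PDEAE denominators in the table shells, one disposition entry and one footnote. PDEAE percentages may look slightly less favourable. With the split shown, a reader can see how many subjects were followed and judge how far the percentage might be off in either direction.

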14.7. Safety and Tolerability Analyses

All safety assessments will be summarized using descriptive statistics. Reported AE terms will be coded using the Medical Dictionary for Regulatory Activities (MedDRA).

Treatment-emergent AEs (TEAEs) will be defined as AEs that occur or worsen after the first dose of study drug. The incidence of TEAEs will be summarized by System Organ Classes and

Preferred Terms and by severity and relationship to study drug. Subjects with SAEs and AEs leading to discontinuation from the study will be summarized. The number and percentage of subjects with C-SSRS assessments at post-baseline will be summarized. Concomitant medications will be categorized using the World Health Organization (WHO) Anatomical Therapeutic Chemical (ATC) classification system. Listings will be provided for all concomitant medications.

Further details will be described in the Statistical Analysis Plan.

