3.2.3. Disposition

Subject disposition will be summarized for all subjects. The number and percentage of subjects will be summarized for the following:

- Subjects who enrolled in the study
- Subjects in the Safety Population
- Subject who completed treatment (as indicated on the case report form (CRF))
- Subjects who completed the study (as indicated on the CRF)
- Subjects who discontinued from the study

For subjects who prematurely discontinue from the study, the reasons for discontinuation as recorded on the disposition CRF will be presented. Percentage will be calculated based on Safety Population.

A listing of disposition for all subjects will be provided.

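### AE-discontinuation tables are keyed to leaving the study and assigned to a period by that date, so an on-treatment AE that ended dosing can be counted as post-discontinuation

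*SAP*

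**What the plan says.** SAP 3.6.2 lists two tables on this subject: "AEs leading to study discontinuation by System Organ Class and Preferred Term", and the same by preferred term only. Both are produced for the treatment period and for the Post-discontinuation Safety Period. The period is set by the date of the discontinuation and not by AE onset: "the AEs will be summarized in the period in which the discontinuation or death occurred". The SAP follows protocol 14.7 in keying the summary to the study: "Subjects with SAEs and AEs leading to discontinuation from the study will be summarized".

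SAP 3.2.2 runs the Treatment Period from Visit 1 to the last dose date plus 1 day. The post-discontinuation period runs from the last dose date plus 2 days to the end-of-study date.

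SAP 3.2.3 counts completion of treatment and completion of the study in separate rows, both read from the CRF and neither defined. Reasons are given for one group only: "For subjects who prematurely discontinue from the study, the reasons for discontinuation as recorded on the disposition CRF will be presented". There is no row for discontinuing treatment.

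Protocol 13.4 has the investigator assess, for every AE, "the intensity (severity) of the event, action taken, and subject outcome". No table listed in the SAP uses the action taken.

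**The concern.** The only objective is long-term safety and tolerability, and the number of subjects who stop the drug because of an AE while taking it bears directly on that objective. The plan does not tabulate this quantity. It tabulates AEs that led to leaving the study, and places them by the date of leaving.

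That date can lie outside the Treatment Period even when the AE began, and dosing ended, inside it. The error between periods goes one way. An AE cannot begin after the discontinuation it caused, so events can move from the treatment table to the post-discontinuation table but not back.

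Other planned outputs do not make up for this. The protocol synopsis expects treatment of about 16 to 68 weeks depending on enrolment date, so short exposure does not identify an early stopper. Adherence under SAP 3.5 is computed only up to the last dose. The treatment-completion row gives a count without reasons.

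**Working it through.** The plan states no figure on this point, and the planned number of up to 250 subjects is not formula-based, so there is nothing to reproduce. The check compares the date rules and then illustrates the effect.

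**Inputs**
- Treatment Period ends at last dose + 1 day; post-discontinuation period starts at last dose + 2 days (SAP 3.2.2).
- TEAEs are classified by onset or worsening within the Treatment Period (SAP 3.6.2).
- AEs leading to study discontinuation are classified by the date of discontinuation (SAP 3.6.2).
- The ET visit should be near the last dose, with no day limit in the text of protocol 7.3 or in the footnote to the schedule in protocol 8.2.
- The Safety Follow-up visit is 14 (±4) days after the final dose (protocol 8.2), that is 14 − 4 = 10 to 14 + 4 = 18 days after it.
- The dates of study discontinuation and end of study are not defined in either document.

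**One hypothetical subject.** AE onset is Day 35 and the last dose is Day 40, stopped because of that AE. The Treatment Period ends on Day 40 + 1 = 41, and the post-discontinuation period starts on Day 40 + 2 = 42.

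| Date recorded as study discontinuation | Day | Period in the AE-discontinuation tables |
|---|---|---|
| Last dose | 40 | Treatment |
| ET visit, 1 day later | 41 | Treatment |
| ET visit, 3 days later | 43 | Post-discontinuation |
| Follow-up visit | 50 to 58 | Post-discontinuation |

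Any date taken from a follow-up visit within its window falls in the later period, since the shortest gap is 10 days. An ET date falls there once the gap is 2 days or more. In every row the same AE is a treatment-period TEAE, because that classification uses onset. The two sets of tables can therefore place one event in different periods.

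**Illustrative size, both inputs assumed.** Let N = 250, r the share of subjects who stop the drug for an AE, and f the share of those dated in the later period. The treatment-period table shows N × r × (1 − f). For r = 8%, 250 × 0.08 = 20 subjects; intervals are exact Clopper-Pearson 95%.

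| f | Treatment-period count | % of 250 (95% CI) | Moved to the later period |
|---|---|---|---|
| 0% | 20 | 8.0 (5.0 to 12.1) | 0 |
| 25% | 15 | 6.0 (3.4 to 9.7) | 5 |
| 50% | 10 | 4.0 (1.9 to 7.2) | 10 |
| 100% | 0 | 0 (0 to 1.5) | 20 |

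At f = 50%, r = 4% goes from 10 (4.0%) to 5 (2.0%), and r = 12% goes from 30 (12.0%) to 15 (6.0%). The documents give no value for r or f, and f = 0 is possible.

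**Coding as a study completer.** If an early stopper were coded this way, the AE would be absent from the AE-discontinuation tables of both periods. The treatment-period arithmetic is the same, with f the share so coded, but nothing reappears in the later table.

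**The case against.** The strongest reply is that the protocol has no path for stopping the drug while remaining in the study. Section 13.4 describes an AE withdrawal as withdrawal from the study. Section 9.5, on stopping rules, refers only to the study-discontinuation procedure in 7.3. Pregnancy is described as stopping the drug in 8.4.1 and as leaving the study in 8.3.7, as if these were one event. If sites date study discontinuation at the last dose, the planned tables are correct.

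This disposes of a stronger reading that a reader might infer: that a subject who stops for an AE and attends follow-up becomes a study completer and drops out of the tolerability results. Protocol 8.2 says: "Subjects who discontinue from the study prematurely will be encouraged to return for an Early Termination visit and a 2-week postdiscontinuation Follow-up visit". Those who return are already study discontinuers, and attendance does not change that. The two completion rows do not show otherwise. They are equally explained by subjects who finish treatment and miss follow-up, and SAP 3.2.1 provides for subjects whose final visit was the last one on treatment. Neither document names a main tolerability result. The AE would also remain in the TEAE tables, if treatment-emergent, and in the listings.

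The reply does not settle the dating question. Treating the two events as one does not say which date is recorded, and the period rule has a purpose only if the discontinuation can fall after the Treatment Period. The CRF, dataset specifications and mock tables are separate documents, not available here, and may settle it. On their present text, the protocol and SAP do not.

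**Conclusion.** The point holds in a limited form. The plan has no table of AEs that led to stopping ALKS 5461. Its substitute places events by a date that is undefined and can fall 2 or more days after the last dose. Where it does, an on-treatment AE that ended dosing is reported as post-discontinuation and the treatment-period figure is too low.

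This assumes that some sites, or the derivation, take the discontinuation date from the ET or follow-up visit. Coding early stoppers as study completers is a further risk, because the completion flags are undefined, but the protocol does not set up that path. The documents support no estimate of either effect, and both may be zero. The change is worth making because it is cheap and removes the dependence on how a form is dated.

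**What to change.** In SAP 3.6.2:
- Keep the study-discontinuation summary, which protocol 14.7 requires.
- Add *TEAEs leading to permanent discontinuation of ALKS 5461*, by SOC and preferred term and by preferred term alone. Derive it from the AE action taken or from the disposition reason, and assign each event to a period by AE onset. Use of the action-taken field assumes that it has a drug-withdrawn option, which the protocol does not state.

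In SAP 3.2.3:
- Add a row for discontinued treatment, with reasons, whether or not the subject attended follow-up.
- State that attending the ET or follow-up visit does not make an early stopper a study completer.

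Protocol 14.7 leaves further detail to the SAP, so an added table is consistent with it. The cost is one derived flag and two extra tables, plus the disposition row. The reported on-treatment AE-discontinuation rate may become slightly less favourable. If the CRF already dates the two events together, the new tables should largely match the existing treatment-period ones and nothing is lost.
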